9.5.6.6 Exceptions from expedited reporting of SAEs

An event need not to be reported as an SAE if it represents only a relapse or an expected change, or progression of a pre-existing condition and is without any other symptoms or signs than those present before treatment. This event needs only to be reported as an AE and should be described in the Study Protocol.

AEs must be followed up until resolution or the follow-up assessment, whichever comes first. At the Follow-up Visit, information on new AEs, if any, and stop dates for previously reported AEs must be recorded.

It is the responsibility of the Investigator to follow up on all SAEs until the subject has recovered, stabilized, or recovered with sequelae, and to report to SBH all relevant new information using the same procedures and timelines as those for the initial report. Relevant information includes discharge summaries, autopsy reports, and medical consultation.

SAEs spontaneously reported by a subject to the Investigator within 30 days after the last follow-up assessment should be reported to SBH even after the clinical investigation has been finished,

if, in the judgment of the Investigator, there might be an association between the event and the previous use of the IMP or as a result of the investigation procedures.

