9.5.6 Adverse events

9.5.6.1 Definitions

Adverse Event (AE)

An AE is any untoward medical occurrence in a clinical study subject administered a pharmaceutical product and which does not necessarily have a causal relationship with this treatment. An AE can therefore be any unfavourable and unintended sign (including clinically significant abnormal values from relevant tests, such as ECGs, vital signs), symptom, or disease temporally associated with the use of an IMP, regardless of whether it is considered related to the IMP.

A *baseline event* is any medical event in a clinical study subject that occurs after signing the ICF up until the (first) administration of IMP.

Clarifications:

Diagnostic and therapeutic non-invasive and invasive procedures, such as surgery, should not be reported as AEs. However, the medical condition for which the procedure was performed should be reported if it meets the definition of an AE. For example, an acute appendicitis that begins during the AE reporting period should be reported as “acute appendicitis” and the resulting appendectomy noticed under *Comments*. Pre-study conditions, which led to elective surgery during the time of the study, are not to be reported as AEs.

If an abnormal vital sign is associated with corresponding clinical signs and symptoms, the sign/symptom should be reported as the AE and the associated laboratory result or vital sign should be considered additional information that is to be collected in the e-CRF.

Serious Adverse Event (SAE)

An SAE is any AE that:

- results in death
- is life-threatening (this refers to an event in which the subject was at risk of death at the time of the event; it does not refer to an event that hypothetically might have caused death had it been more severe)
- requires inpatient hospitalisation or prolongation of existing hospitalisation
- results in persistent or significant disability/incapacity
- is a congenital anomaly/birth defect
- is medically important (this refers to an event that may not be immediately life-threatening or result in death or hospitalisation, but may jeopardise the subject or may require intervention to prevent any of the SAEs defined above)

Examples of medically important events are intensive treatment in an emergency room for allergic bronchospasm or blood dyscrasias, convulsions that do not result in hospitalisation, development of drug dependency and drug abuse.

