Planned hospitalisations or surgical interventions for a condition that existed before the subject signed the ICF and that did not change in intensity are not SAEs.

If there is any doubt as to whether an AE meets the definition of an SAE, a conservative viewpoint must be taken, and the AE must be reported as an SAE.

Serious Adverse Reaction (SAR)

The term SAR is to be used whenever either the Investigator or SBH or designee assessed the SAE as possibly or probably related to the IMP.

Suspected Unexpected Serious Adverse Reaction (SUSAR)

A SUSAR is any SAR whose nature or intensity is not consistent with the current version of the Investigator's Brochure (IB).

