9.5.6.5 Collecting and recording of AEs

AEs and baseline events identified using any of the following methods will be recorded:

- AEs spontaneously reported by the subject
- AEs observed by the Investigator or medical personnel
- AEs elicited based on non-leading questions from the Investigator or medical personnel
- AEs obtained from Subject Diaries, as described in section 9.5.4.3

Collection of baseline events starts after the subject signs the ICF and continues until the first intervention with the IMP.

AE collection starts with the first intervention with the IMP and continues until the last follow-up assessment. Any AE with start date on the day of first IMP intervention must be recorded with start time.

At the Follow-up Visit, information on new AEs or SAEs, if any, and stop dates for AEs recorded and on-going during the dosing period must be recorded.

All AEs, serious and non-serious, should be recorded in the CRFs. Reporting of SAEs

No distinction should be made between the investigational product and the reference product regarding reporting of SAEs as long as the code is not broken.

Starting from administration of first dose of IMP, all SAEs must be reported by the Investigator to [REDACTED] Pharmacovigilance, the Monitor and SBH within 24 hours of knowledge of the event, regardless of the time that may have elapsed from the time the event occurred to when the Investigator first learns of it.

All SAEs should be reported to [REDACTED] Pharmacovigilance:

E-mail: [contact]

The Initial Report should contain as a minimum the following information:

- Subject identification
- Treatment specification (to be expressed in a blinded fashion, e.g. “Treatment A/Treatment B”)
- AE diagnosis
- Time specification for the medical event
- Name of the original reporter
- Seriousness classification

A Serious Adverse Event Report Form must also be completed, signed by the Investigator and submitted to [REDACTED] Pharmacovigilance, the Monitor and Sponsor no later than three calendar days after the initial information was received. Apart from the information above, this Follow-up Report should also contain the following information:

- assessment of severity
- assessment of causality

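### Section 9.5.6.6 lets a serious relapse or progression of a pre-existing condition, if it brings no new symptoms or signs, be reported only as an AE, in conflict with Sections 9.5.6.1 and 9.5.6.5

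*Combined protocol and SAP*

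**What the plan says.** Section 9.5.6.1 defines an SAE by a list of seriousness criteria, one of which is that the event "requires inpatient hospitalisation or prolongation of existing hospitalisation". The list makes no exception for conditions the subject already had. The section then gives one exclusion from SAE status: "Planned hospitalisations or surgical interventions for a condition that existed before the subject signed the ICF and that did not change in intensity". Where it is doubtful whether an AE meets the definition, "a conservative viewpoint must be taken, and the AE must be reported as an SAE".

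Section 9.5.6.5 covers reporting. From the first dose, "all SAEs must be reported by the Investigator to" pharmacovigilance, the Monitor and the sponsor within 24 hours of becoming aware of the event. It refers to no exception.

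Section 9.5.6.6 opens with one. Under it, an AE "need not to be reported as an SAE if it represents only a relapse or an expected change, or progression of a pre-existing condition", with the added condition "and is without any other symptoms or signs than those present before treatment". It continues: "This event needs only to be reported as an AE and should be described in the Study Protocol".

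**The concern.** The exception in Section 9.5.6.6 is wider than the exclusion in Section 9.5.6.1, and neither section mentions the other. Section 9.5.6.1 releases planned procedures for a condition of unchanged intensity. Section 9.5.6.6 releases relapse and progression, which usually mean that the condition has changed and which may lead to an unplanned admission. It does not say that the event must be non-serious or judged unrelated to the vaccine.

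At stake is the handling of an event that meets the protocol's own definition of an SAE. If the site follows Section 9.5.6.6, the 24-hour notice is not sent. SAR status under Section 9.5.6.1 starts from an SAE that the Investigator or the sponsor considers related, and SUSAR status starts from a SAR. An event that reaches the sponsor only as a CRF entry may therefore never be put to the sponsor's assessment. Follow-up may also be shorter: Section 9.5.6.6 follows SAEs until the subject has recovered or stabilised, but ordinary AEs no further than the follow-up assessment.

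**Working it through.** No figure in the plan bears on this point, so there is nothing to recompute. The check is to take the kinds of event that could arise and apply each section in turn.

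| Event after first dose | Section 9.5.6.1 | Section 9.5.6.5 | Section 9.5.6.6 | Result |
|---|---|---|---|---|
| (a) Unplanned admission; pre-existing condition worse; no new symptoms or signs | SAE | 24-hour report | AE only is allowed | Conflict |
| (b) Admission for a flare with any new symptom or sign | SAE | 24-hour report | Exception does not apply | No conflict |
| (c) Planned admission; intensity unchanged | Not an SAE | Not applicable | Not needed | No conflict |
| (d) Doubt whether a seriousness criterion is met | Treat as SAE | 24-hour report | Displaced by the doubt rule | No conflict in practice |

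Three details confirm that case (a) is a true conflict.

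1. *The limiting condition does not remove it.* Section 9.5.6.6 asks which symptoms and signs are present. Section 9.5.6.1 asks whether the condition changed in intensity. The same symptoms in a more severe form pass the first test and fail the second.
2. *The doubt rule does not remove it.* That rule concerns doubt about whether the definition is met. In case (a) an unplanned inpatient admission plainly meets it.
3. *The heading does not remove it.* The heading of Section 9.5.6.6 speaks of expedited reporting, a term that Section 9.5.6.5 uses for SUSARs. The text goes further and says the event need be reported only as an AE.

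The clarification in Section 9.5.6.1 that keeps pre-study conditions leading to elective surgery out of AE reporting does not help either, because it also concerns elective procedures.

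The requirement that exempted events be described in the protocol is not met anywhere: no section lists a condition or event to which the exception applies. A site therefore cannot tell what was meant to be covered.

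**The case against.** The best reply is that this is a deliberate and narrow exception. It is permissive, since an Investigator may still report the event as an SAE. It excludes any flare with a new symptom or sign. It does not amend the definition in Section 9.5.6.1, so an exempted event could still count as an SAE for follow-up and for the SAE tables in Section 9.7.2.2. Because no exempt events are listed, it can be argued that nothing qualifies. For a condition that was quiescent at dosing, it can also be argued that a relapse brings symptoms that were not present before treatment. Further detail sits in a Safety Management Plan that is not among the documents. All of this stands, and it narrows the point. It also shows that the outcome depends on how a site reads the clause, which is a reason to reconcile the text.

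Four stronger readings are tempting, and the documents do not support them.

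- *Any post-dose flare would escape the 24-hour report.* It would not: the condition on symptoms and signs keeps case (b) in the SAE route.
- *SAE reporting is the only prompt safety information*, because there is no safety committee (Sections 9.1.3 and 9.7.5.7) and no safety laboratory testing (Section 9.5.3). This overlooks several provisions. All AEs go into the CRF (9.5.6.5), promptly (9.8.2) and under electronic monitoring (9.8.1). The Investigator assesses causality for each AE (9.5.6.3). The blinded Monitor checks SAE reporting with access to clinical records (9.6.1). Eligibility is checked again before Dose 2 (9.3.4 and 9.3.5).
- *The vaccine is expected to provoke flares of quiet conditions.* Section 7.3.2 expects only infrequent, mild and transient symptoms, and exclusion criterion 1 removes conditions that the Investigator judges unsafe or likely to interfere with the evaluation of responses, naming gastrointestinal and autoimmune disease.
- *The SAE count would be understated by some percentage.* The documents give no SAE rate and no probability of an exempt event, so no such figure can be derived.

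**Conclusion.** The conflict is real but narrow. For an unplanned admission caused by worsening of a pre-existing condition without new symptoms or signs, Sections 9.5.6.1 and 9.5.6.5 require an SAE report within 24 hours, while Section 9.5.6.6 accepts an AE entry alone. Loss of the 24-hour report follows directly if the exception is used. Loss of the sponsor's SAR/SUSAR assessment, of SAE follow-up and of a place in the SAE tables is possible rather than certain, because it depends on whether the exception is read as changing the event's status or only its reporting.

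The size cannot be put in numbers. Such events are probably few: the 280 planned subjects are healthy volunteers, relevant conditions are excluded, and AE collection in the main study covers roughly 3 to 5 weeks (2 to 4 weeks of treatment plus 1 week of follow-up, from the synopsis). Exclusion criterion 1 depends on the Investigator's judgement, however, so subjects with an accepted prior condition can enter. The primary endpoint, sample size and non-inferiority analysis are not affected. The case for a change rests on the clarity of safety reporting and the low cost of the correction.

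**What to change.** Reconcile Sections 9.5.6.1, 9.5.6.5 and 9.5.6.6 in one of two ways:

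- delete the first paragraph of Section 9.5.6.6; or
- keep it, but state that it applies only to events that meet no seriousness criterion.

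Either way, the exclusion for planned procedures in Section 9.5.6.1 becomes the only one, and relatedness and expectedness are judged at the SAR and SUSAR steps. If the paragraph is kept, it should also name the events it covers, as its own text requires, or drop that requirement. The Safety Management Plan should be brought into line. The cost is one paragraph in a protocol amendment, the matching text in that plan, and possibly a few extra SAE forms.

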9.5.6.7 Procedures in case of pregnancy

In case of pregnancy or suspicion of possible pregnancy, the subject must be discontinued from further dosing in the study. Pregnancy itself is not regarded as an AE unless there is a suspicion that the IMP may have interfered with the effectiveness of the contraceptive medication. However, the outcome of all pregnancies (spontaneous miscarriage, elective termination, normal birth or congenital abnormality) must be followed up and documented even after the Subject was discontinued from the study.

All events of congenital abnormalities/birth defects are SAEs. Spontaneous miscarriages should also be reported and handled as AEs. Any pregnancy revealed during the study must be reported to SBH and the Monitor on the pregnancy report form. All outcomes of pregnancy must be reported to SBH and the Monitor on the pregnancy outcomes report form.

9.5.6.8 Coding of AEs

All AEs will be coded according to Medical Dictionary for Regulatory Activities (MedDRA) by [REDACTED].

9.5.7 Appropriateness of measurements

Standard safety assessment methods are used in this study and are very similar to procedures performed to monitor vaccine safety in a previous Phase IIb study of adult Finnish travellers before they left Finland to go to Benin in West Africa (OEV-123, EudraCT No.: 2016-002690-35).

Due to difficulties to get a reliable measurement of immune responses to ETEC CFs in serum of non-primed (i.e. previously not immunized nor infected) Swedish individuals, only the immune response rates to LTB will be measured. For oral vaccines, the responses are evoked in the gut and only some immune responses, e.g. against LTB for ETVAX[®], are detectable in serum of immunised individuals [6, 12]. Serum IgA responses to LTB correlate significantly with IgA responses measured in mucosal samples [12]. LTB-specific serum antibody levels measured by ELISA also closely reflect the neutralization capacity of the serum antibodies [12]. ELISA assays to measure LTB-specific IgA and IgG antibodies are well-established and have previously been used to evaluate antibody responses induced by ETVAX[®] vaccination in Swedish volunteers and in Bangladeshi adults and children [11-15]. The ELISA method used to measure antibodies in this trial has been validated by comparisons with ECL assays in previous studies [14]. Exploratory analyses of serum antibodies will also be performed using the ECL method. A cut-off of 2 for seroconversion has been used in many previous studies of oral vaccines, including all previous trials of ETVAX[®].

9.6 Data quality assurance

This study will be conducted in compliance with the protocol, relevant Standard Operating Procedures (SOPs), Good Clinical Practice (GCP) and the applicable regulatory requirement(s).

The Principal Investigator will provide SBH with all data produced during the study from the scheduled study assessments. He/she ensures the accuracy, completeness, legibility, and timeliness of the data reported to SBH in the CRF and in all required reports.

9.6.1 Monitoring

The investigational site will be visited both by the *blinded* Monitor and/or the *blinded* [REDACTED] Project Manager overseeing monitoring activities, as well as the *unblinded* Monitor periodically at times agreed on by the Investigator. It is the function of the Monitor to ascertain that all aspects of the CSP are complied with and that the conduct of the investigation conforms to applicable regulatory requirements and established rules for GCP.

At the time of each monitoring visit, the *blinded* Monitor will review the CRFs to ascertain that all items have been completed and that the data provided are accurate and obtained in the manner specified in the CSP.

The *blinded* Monitor will also check that the data in the CRF are consistent with the clinical records (Source Data Verification) and that investigational results are recorded completely and correctly.

The *blinded* Monitor will check on the reporting of SAEs and record keeping. For this purpose, the Monitor must be given direct access to clinical records, original laboratory data, etc., as far as these relate to the investigation and without jeopardizing subject integrity. CRFs for all included subjects must be made available to the *blinded* Monitor for review.

The *unblinded* Monitor will visit the investigational site to review documents and records related to the preparation of the vaccine, i.e. information unblinded to treatment allocation.

A risk-based approach will be developed for the monitoring visits. Further details are provided in a separate Monitoring Plan.

9.6.2 Audits and inspections

Authorized representatives of SBH or a Competent Authority (e.g. LV), may perform audits or inspections at the research clinic, including Source Data Verification (SDV). The purpose of an audit or inspection is to systematically and independently examine all study-related activities and documents, to determine whether these activities were conducted, and data were recorded, analysed, and accurately reported according to the protocol, ICH-GCP guidelines and any applicable regulatory requirements. The Investigator will contact SBH immediately if contacted by a Competent Authority about an inspection at the centre.

The Investigator is required to inform SBH immediately of an inspection requested by the Competent Authority (e.g. LV).

9.6.3 Case Report Forms (CRFs)

A CRF must be completed and signed by authorized personnel for each included subject, according to the CRF completion instructions.

All data must be entered in English. The CRFs should always reflect the latest observations made during the subject's participating in the study. Therefore, the CRFs should be completed as soon as possible during or after the subject's visit.

The Investigator must verify that all data entries in the CRFs are accurate and correct by signing the completed CRF.

The completed CRFs should be made available for checking of completeness and accuracy by the *blinded* Monitor.

Please see section 9.8 for further details.

9.6.4 Source Data

A separate source data document will be generated for the site before start of enrolment, specifying the location of the source of derived information appearing in the CRF. This document must be signed by the Principal Investigator and the Monitor to confirm agreement before start of recruitment.

The Investigator should guarantee access to source documents to the Monitor, Competent Authority (LV) and the IEC (EPM), if required.

9.6.5 Training of study staff

Before inclusion of the first investigational subject the Monitor (both *blinded* and *unblinded*) and/or Project Manager will perform an initiation visit at the investigational site. The requirements of the Clinical Study Protocol and related documents will be reviewed and discussed, and the investigational staff will be trained in any study specific procedures and system(s) utilised.

It is the responsibility of the Principal Investigator to ensure that all personnel involved in the study are fully informed of all relevant aspects of the study, and have a detailed knowledge of and training in the procedures that are to be executed by them, including good documentation practice. Any new information of relevance to the performance of this study must be forwarded to the staff involved in a timely manner.

The Investigator will keep a list of all personnel involved in the study together with their function and study related duties delegated. A Curriculum Vitae (CV) will be available for all staff delegated study-specific duties.

9.7 Statistical methods and determination of sample size

General descriptive statistics for categorial variables will be number of observations (n) and proportion (%) within treatment group. General descriptive statistics for continuous variables will be number of observations (n), Mean, Quartile 1 (Q1), Median, Quartile 3 (Q3), Geometric Mean, Standard deviation (SD) and Range (Min, Max).

A detailed statistical analysis plan (SAP) will be written and finalized well in advance of database lock. The plan will follow the outline of the statistical analyses presented below, but details necessary to complete the statistical analyses will be given.

9.7.1 Description of study population

9.7.1.1 Demographics and baseline characteristics

Descriptive statistics of demographics and other baseline characteristics will be presented for each vaccination group.

9.7.1.2 Medical/surgical history and concomitant medication

Medical/surgical history and prior/concomitant medications will be presented by descriptive statistics for each vaccination group.

9.7.1.3 Analysis of efficacy (Seroconversion rates of IgA and/or IgG anti-LTB antibodies in serum)

The primary endpoint, response, will be defined as “yes” for patients with at least a 2-fold increase in IgA and/or IgG antibody levels against LTB in serum between pre- and post-immunization samples (Visit 4 versus Visit 2).

The response rates (seroconversion rates) within treatment groups, p_{wet} and $p_{partially_dried}$, will be estimated as the proportion of responders (response = “yes”) in each treatment group. The primary analysis of the study seeks to compare the seroconversion rates using the difference

$$d = p_{partially_dried} - p_{wet}$$

The following non-inferiority hypothesis will be tested, using a -15% non-inferiority limit (on an absolute scale):

H_0 : The seroconversion rate of the partially dried group is lower than that of the wet group, $d < -0.15$

H_A : The seroconversion rate of the partially dried group is higher than or equal to that of the wet group, $d \geq -0.15$

A two-sided 95% confidence interval (CI) for d will be calculated by normal approximation. The lower limit of the CI will be compared to the non-inferiority limit -0.15. If the lower CI limit is larger than or equal to the non-inferiority limit, the null hypothesis will be rejected, and the result will be taken as supporting non-inferiority of the partially dried formulation compared to the wet formulation.

The normal approximation requires at least 5 patients in each cell of the Treatment by Vaccine response contingency table. If assumptions are not fulfilled, a non-parametric CI will be used instead.

The primary endpoint will be summarized for the full analysis set (FAS) and the per protocol analysis set (PPAS). The primary endpoint analysis of PPAS will be considered the primary analysis of the study.

The primary endpoint, i.e. the proportion of responders with at least a 2-fold increase in LTB-specific IgA and/or IgG antibody levels, will be summarized with descriptive statistics for the

PPAS and FAS. In addition, the proportion of responders with at least a 4-fold increase in IgA and/or IgG antibody levels will be presented. The levels of serum antibodies at visit 2 and visit 4 and the fold rise (magnitude of response) will also be presented for both IgA and IgG.

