8 STUDY OBJECTIVES AND ENDPOINTS

8.1 Primary objective

The aim of this study is to demonstrate non-inferiority, in terms of immunogenicity, between the “wet formulation” and the newly developed partially dried formulation of selected

components of ETVAX[®].

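### Do the worded hypotheses, which leave out the 15-point margin, let a positive result claim more than the test shows?

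*Combined protocol and SAP*

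**What the plan says.** Section 9.7.1.3 defines d as the seroconversion rate in the partially dried group minus that in the wet group. It introduces the hypotheses with "The following non-inferiority hypothesis will be tested, using a -15% non-inferiority limit (on an absolute scale". Two lines follow, each with a sentence and an inequality:

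- H0: "The seroconversion rate of the partially dried group is lower than that of the wet group", with d < -0.15.
- HA: "The seroconversion rate of the partially dried group is higher than or equal to that of the wet group", with d ≥ -0.15.

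The decision rule comes next, built on a two-sided 95% normal-approximation interval for d: "The lower limit of the CI will be compared to the non-inferiority limit -0.15". A lower limit at or above that value rejects H0. The section then says what a rejection means: "the result will be taken as supporting non-inferiority of the partially dried formulation compared to the wet formulation".

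Section 8.1 gives the primary objective: "The aim of this study is to demonstrate non-inferiority, in terms of immunogenicity". Section 9.7.4.3 sizes the trial for a -15-point margin with 85% seroconversion in both arms: 126 per arm for 90% power, or 140 per arm after 10% dropout. Section 9.2 justifies the 15% margin and says that a finding of non-inferiority would support moving to Phase 3 efficacy trials.

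**The concern.** Read without the inequalities, the two sentences describe a different trial. H0 would be d < 0 and HA would be d ≥ 0, so rejecting H0 would mean that the dried formulation seroconverts at least as often as the wet one. The test cannot show that. A true deficit of 5 or 10 points satisfies the worded H0 and the printed HA at the same time, and deficits of that kind are what a non-inferiority margin exists to allow.

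This is the only confirmatory hypothesis (section 9.7.5.4), and section 9.7 says the detailed SAP will follow the protocol's outline. If the sentence were copied into the SAP and the report, a reader could take a positive result as equality or better when the test had only excluded a deficit of more than 15 points. The trial is meant to support a Phase 3 decision, where those two messages differ materially.

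A smaller point is that d = -0.15 is placed in the alternative, and a lower limit exactly equal to -0.15 counts as success. The usual convention puts the margin value in the null.

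**Working it through.** **1. Which hypothesis was the trial sized for?** Inputs from section 9.7.4.3: 85% in both arms, margin -0.15, two-sided 95% interval (one-sided 0.025), 90% power, Farrington-Manning method.

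The restricted maximum-likelihood rates under d = -0.15 are 0.7489 (dried) and 0.8989 (wet).

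- Standard deviation under the null: s0 = √(0.7489 × 0.2511 + 0.8989 × 0.1011) = 0.5282
- Standard deviation under the alternative: s1 = √(2 × 0.85 × 0.15) = 0.5050
- n per arm = [(1.960 × s0 + 1.2816 × s1) / 0.15]² = (1.6823 / 0.15)² = 125.79, rounded up to 126
- Power at 126 per arm: 90.05%
- With dropout: 126 / 0.90 = 140

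The plan's figures reproduce, and they reproduce for the formula.

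**2. What would the words imply?** These are exact binomial probabilities for the 95% Wald interval, 126 per arm and 85% in both arms.

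| Lower limit must reach | Chance of success at d = 0 |
|---|---|
| -0.15 (formula) | 91.7% |
| 0 (words) | 2.7% |

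A trial planned for 90% power cannot have been meant to have 2.7%, so the words are not the intended hypothesis.

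**3. How does the -0.15 rule behave when the dried formulation is worse?** Same method, wet rate 85%.

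| True d | Chance H0 is rejected |
|---|---|
| 0 | 91.7% |
| -5 points | 56.2% |
| -7.5 points | 34.3% |
| -10 points | 17.4% |
| -15 points | 2.6% |

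With a wet rate of 93% (the earlier Swedish result in section 7.2.5.2) the chances are about 77% at -5 points and 25% at -10. These two are approximate, because section 9.7.1.3 switches to another interval when a cell has fewer than 5 subjects.

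In every row with d below 0, the worded HA is false when H0 is rejected. But any 15-point non-inferiority test of this size behaves this way, and the table would be the same with reworded sentences. The last row, at the margin, is the type I error: 2.6% against a nominal 2.5%.

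**4. A concrete result.** Dried 100/126 (79.4%), wet 107/126 (84.9%).

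- d = -7/126 = -0.0556
- Standard error = √[(0.7937 × 0.2063 + 0.8492 × 0.1508) / 126] = 0.0481
- 95% interval: -0.1499 to +0.0388

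The rule is met with a lower observed rate on the dried formulation. Under section 9.7.1.3 this is reported as supporting non-inferiority, which is correct. The worded HA would describe it wrongly.

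**5. The boundary.** Over all pairs of responder counts with equal arms of 120, 126, 130, 135 or 140, no pair gives a lower Wald limit equal to -0.15. At 126 per arm, "at least" and "greater than" give identical probabilities in every scenario above.

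**6. Words against the rest of the plan.**

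| Element | Dividing line |
|---|---|
| Sentences for H0 and HA | 0 |
| Introduction to the hypotheses | -15% |
| Inequalities on the same two lines | -0.15 |
| Confidence-interval rule | -0.15 |
| Stated conclusion on rejection | Non-inferiority |
| Objective (section 8.1) | Non-inferiority |
| Sample size (section 9.7.4.3) | -15 points |

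**The case for a change.** The best case for a change is that a primary hypothesis should be right in words as well as in symbols. The contradiction is on the face of the text, affects both H0 and HA, and is not an extraction fault. Misreading is not far-fetched either: with equal true rates of 85%, about 38% of trials would meet the rule with an observed dried rate below the wet rate, and the sentence would then misdescribe the data. The correction would be a few words and cost nothing.

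The inconsistency itself stands. The step from there to a wrong claim does not, because the same section says what rejection supports, and that is non-inferiority. An equality or superiority claim would have to override the plan's own conclusion, its label and its objective. The rejection probabilities describe the chosen margin and do not measure any effect of the wording. The boundary point is a matter of convention and changes no decision at the sample sizes checked.

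**Conclusion.** The concern does not call for a change. The sentences for H0 and HA omit the margin and contradict the inequalities beside them, which is a clerical slip. An analyst following section 9.7.1.3 can run only one test, comparing the lower 95% limit with -0.15, and the conclusion prescribed for it is the correct one. The effect of the slip on type I error, power, sample size, decision threshold and stated conclusion is nil.

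This rests on the report using the conclusion given in section 9.7.1.3. The detailed SAP announced in section 9.7 was not available for this review, so its wording could not be checked. The rejection probabilities assume 126 evaluable subjects per arm, the Wald interval and, unless stated otherwise, a wet rate of 85%.
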